
Methodology: This is a multi-center, randomized, double-blind, placebo-controlled crossover study to evaluate the effect of the isoflavone genistein on the short-term untoward effects of myelosuppressive chemotherapy used to treat pediatric cancers. Newly diagnosed cancer patients aged 1 - 21 years will be registered to the study and informed consent will be obtained prior to any study-related procedures. Stratification will be based on length of chemotherapy cycles: 14 days or 21 days. Subjects will be randomized 1:1 to one of two schedules within each stratum:
 
Arm A: Subjects will receive genistein daily throughout chemotherapy Cycles 1 and 2, and placebo during chemotherapy Cycles 3 and 4
 
Arm B: Subjects will receive placebo daily throughout chemotherapy Cycles 1 and 2, and genistein during chemotherapy Cycles 3 and 4
 
The safety and efficacy of genistein will be assessed during each cycle through clinical laboratory tests, cytokine panels, and physical exams. Study supplement compliance will be monitored by use of a subject diary, drug reconciliation, and serum isoflavone levels. Adverse events will be monitored starting on Cycle 1 Day 1 through 30 days following the last day of study supplementation (genistein/placebo). Serious adverse events will be collected through 6 months post-study intervention.
	
Number of subjects (planned): Up to 50 subjects will be accrued to obtain 44 eligible subjects.	

Main Eligibility Requirements:
 
Inclusion criteria:
 
 New diagnosis of a solid tumor or lymphoma, with histologic verification of malignancy Age 1 - 21 years at the time of diagnosis Able to tolerate enteral medication administration Performance score minimum requirement ≥ 50 on Karnofsky/Lansky scale Planned chemotherapy regimen involves at least four consecutive cycles of chemotherapy that is known to be myelosuppressive 
Exclusion criteria:
 
 Known allergy to soy or any soy-based food or supplement Pre-existing neutropenia or neutrophil qualitative or quantitative disorder Pre-existing cytopenia or bone marrow failure syndrome Subject will not receive myelosuppressive chemotherapy Current acute or chronic leukemia diagnosis Enrolled on another therapeutic or supportive care clinical trial within the last 30 days Secondary malignancy 	

Investigational intervention:

- Genistein: 30 mg/day, oral tablets
- Placebo: oral tablets

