6 EVALUATIONS AND ASSESSMENTS

6.1 Study Procedures and Assessments Table

Table 3: Schedule of Events

Assessment ¹	Pre-Treatment	Treatment Phase				Follow-up ²
	Day -28 to Day 1 ³	Cycle 1 Day 1 ^{3,4}	Cycles 1 - 4 Weekly ⁵	Cycles 2 - 4 Day 1	Cycle 4 Last Day ⁶	
Informed Consent	X					
Eligibility Determination	X					
Baseline ⁷ and Demographic ⁸ Data	X					
Randomization ⁹	X					
Medical History/Baseline Condition	X					
Physical Exam ¹⁰	X	X	X	X		
Height and Weight		X		X		
Chemistry/Metabolic Panel ¹¹	X	X		X		
CBC with Differential ¹²	X		X	X		
CRP, ESR, and Homocysteine ¹³	X			X	X	
Cytokine and Isoflavone Panels ¹⁴		X		X	X	
Audiogram ¹⁵	X			X	X	
Concomitant Medications Review ¹⁶	X ¹⁷	X	X	X	X	
Adverse Events Review		X	X	X	X	X
Study Medication Dispensing		X		X		
Subject Pill Diary ¹⁸		X	X	X	X	
Study Medication Reconciliation				X	X	

¹ All visits and assessments must be completed within ± 72 hours of the milestone date unless otherwise specified.

² Subjects must be followed for 30 days following the last study intervention for AEs and for 6 months for SAEs, unless consent is withdrawn.

³ Cycles begin on Day 1. There is no Day 0.

⁴ Cycle 1 Day 1 assessments do not need to be repeated if completed in the 7 days prior (i.e. Day -7 to Day 1) unless otherwise stated.

⁵ Weekly visits are to occur at 7-day intervals between Day 1 and the cycle's last day.

⁶ The last day of a cycle corresponds to the Day 1 of the next cycle. The last day's number will vary by cycle length.

⁷ Diagnosis, stage, grade, site(s) of disease, anti-neoplastic treatment +/- radiation regimen

⁸ Age, sex, race, and ethnicity

⁹ Randomization must occur within the 2 days prior to the anticipated Cycle 1 Day 1. ([Section 4.5](#))

¹⁰ Full physical exam at the beginning of each cycle of chemotherapy, and a symptom-directed physical exam at each of the weekly treatment visits. Collect height, weight and BSA on Day 1 of each cycle.

¹¹ Chemistry labs to assess for general safety must be conducted on Day 1 of each cycle. They must include serum creatinine, total bilirubin, AST, and ALT.

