6.4 Post-Treatment/Follow-up Assessments

All subjects will be followed for a minimum of 30 days after the last dose of protocol therapy (genistein/placebo) to assess for AEs. If subjects complete all four cycles of anti-neoplastic therapy, this visit will occur at 35 ± 5 days following the last day of Cycle 4. If subjects are withdrawn or discontinued prior to completion of the anti-neoplastic therapy, this will occur at 35 ± 5 days following the last day the study supplement is administered.

All serious adverse events (SAEs), other grade 3 – 4 AEs that are believed to be related to the investigational intervention, cancer progressions and relapses (including date, description, and sites), secondary malignancies (including date, description, and sites), and deaths (with date and clinical narrative) must be reported until 6 months after the end of the study intervention. See [Section 9.2](#) for additional information on AE and SAE reporting during this period.

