9 ADVERSE EVENTS AND REPORTING

After informed consent has been obtained but prior to initiation of investigational intervention, only SAEs caused by a protocol-mandated intervention must be reported (e.g. SAEs related to invasive procedures).

After initiation of the investigational study supplement dosing, all AEs must be collected as described in the following sections through 30 days after the last study supplement dose ([Section 6](#)). In addition, investigators must report any deaths, SAEs, other AEs of concern that are believed to be related to the investigational intervention, cancer progression, cancer relapse, and secondary malignancies through six months after the end of the study intervention. See the Procedure Manual for additional information on and resources for AE reporting.

All AEs, whether reported by the subject or noted by study personnel, must be recorded in the subject's medical and study records. AEs must be assessed for seriousness, severity, attribution and expectedness by the investigator. The following sections provide definitions for AE characteristics and reporting requirements.

AEs must be followed to resolution or stabilization, and reported as SAEs if they are or become serious. This also applies to subjects experiencing AEs that cause interruption or discontinuation of study intervention, or those experiencing AEs that are present at the end of their participation in the study. Such subjects should receive post-treatment follow-up as appropriate.

If an ongoing AE changes in its severity or in its perceived relationship to study intervention, a new AE entry for the event must be completed.

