Table 6. DSMC reporting requirements for AEs that occur after the subject’s last cycle taking the study supplement until 6 months post-treatment (i.e. follow-up)

Attribution to Study Supplement	Grades 1 & 2	Grade 3	Grade 4	Grade 5
	Expected & Unexpected	Expected & Unexpected	Unexpected	Unexpected
Unrelated Unlikely	Not required	Not required	OnCore: 30 days/quarterly ²	See SAE
Possible Probable Definite		OnCore: 30 days from end of Reporting Period ³	OnCore: 15 days from end of Reporting Period ³	
SAE ⁴	OnCore: (24-hrs), 7 days ¹			

¹ Enter into Cancer Center database within 24 hours and submit supporting documentation within 7 days.
² Data to be entered within 30 days of the end of the reporting period or the next quarterly deadline, whichever comes last. Deadlines are Jan. 31, Apr. 31, July 31, and Oct. 31.
³ Reporting is not required if AE onset is > 30 days after the last dose of study supplement
⁴ Any AE that is an SAE must be reported using the SAE timeline regardless of grade or attribution.

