9.2.3.2 Additional Reporting Requirements for Affiliate Sites

In addition to reporting in OnCore, all SAEs must be reported by facsimile within 24 hours of the event to the Sponsor (UVa) as outlined in the Procedure Manual. Any SAEs that occur in the 30 days following the last dose of protocol therapy must be reported. After that time, only SAEs that are related to protocol therapy are required to be reported. For every SAE which occurs, affiliates must send an SAE report with the following information:

- Safety reporting cover sheet (Procedure Manual appendices)
- Relevant hospital case records and autopsy reports (where applicable)

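### Late non-serious related grade 3–4 AEs are reportable to 6 months under Section 6.4 but only to 30 days under Table 6, which keeps unrelated grade 4 events longer than related ones

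*Combined protocol and SAP*

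**What the plan says.** Section 6.4 lists what is to be reported in follow-up, beginning with "All serious adverse events (SAEs), other grade 3 – 4 AEs that are believed to be related to the investigational intervention", and closes the list with "must be reported until 6 months after the end of the study intervention". It then sends the reader to Section 9.2 "for additional information on AE and SAE reporting during this period".

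The opening of Section 9 gives 30 days for AEs in general. It adds a longer list (deaths, SAEs, related other AEs of concern, "cancer progression, cancer relapse, and secondary malignancies through six months after the end of the study intervention"). The protocol does not define an AE of concern.

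Footnote 2 to the Schedule of Events (Section 6.1) divides events by seriousness alone: "Subjects must be followed for 30 days following the last study intervention for AEs and for 6 months for SAEs, unless consent is withdrawn".

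Table 6 in Section 9.2.1 is titled as running to 6 months after treatment. Footnote 3 is attached to its grade 3 and grade 4 cells for possible, probable and definite attribution: "Reporting is not required if AE onset is > 30 days after the last dose of study supplement". The grade 4 cell for unrelated and unlikely attribution carries footnote 2 instead, which sets only a data-entry deadline. The SAE row carries footnote 4, which applies the SAE timeline whatever the grade or attribution.

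Section 9.2.3.2 adds a facsimile to the sponsor for affiliate sites, on top of OnCore entry. Affiliates must report any SAE in the 30 days after the last dose, and then: "After that time, only SAEs that are related to protocol therapy are required to be reported". The Synopsis has no such restriction: "Serious adverse events will be collected through 6 months post-study intervention".

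**The concern.** A site following Section 6.4 would report a related, non-serious grade 3 or 4 event that began, say, two months after the last dose. A site following Table 6 would not. Section 6.4 itself directs readers to Section 9.2, so a careful coordinator is led from one rule to the other with nothing to say which prevails.

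What is at stake is the completeness of late safety data on events that the investigator thinks the supplement may have caused. Section 9.2.3.3 builds the annual FDA report from AEs and SAEs collected as Section 9.2.1 describes, so the Table 6 cut-off would carry into that report.

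The affiliate sentence raises a separate question. Read alone, it lets an affiliate stop reporting unrelated SAEs at 30 days, while Section 6.4, the Synopsis and the Schedule set 6 months for SAEs without regard to attribution.

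**Working it through.** No sample size, power or alpha figure is involved, and the plan gives no number to reproduce. The check sets the rules side by side by event class.

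| Event class in follow-up | 6-month rule | 30-day rule |
|---|---|---|
| Non-serious, related, grade 3–4 | Section 6.4; Section 9, if the event counts as an AE of concern | Table 6 footnote 3; Schedule footnote 2 (all AEs) |
| Non-serious, unrelated or unlikely, grade 4 | Table 6 cell with footnote 2, no onset cut-off | Schedule footnote 2 (all AEs) |
| SAE, related | Section 6.4; Section 9; Synopsis; Schedule footnote 2; Table 6 SAE row; Section 9.2.3.2 | none |
| SAE, not related | Section 6.4; Section 9; Synopsis; Schedule footnote 2; Table 6 SAE row | Section 9.2.3.2, affiliates only, channel unclear |

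1. *Who is affected by footnote 3.* An event that is serious goes through the SAE row under footnote 4 and stays reportable to 6 months. Footnote 3 therefore bites only on non-serious events.

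2. *Whether the grade 4 cells apply.* The grade 4 column covers unexpected events only. Section 9.2.1 defines expectedness by reference to genistein treatment, and Section 5.1.7 names abdominal pain of grade 2 or lower as the only expected event. Every grade 4 event is therefore unexpected and falls in that column.

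3. *Whether the class can contain events.* Section 7.1 treats an ANC below 500 cells/µl as grade 4 on the count alone, so a grade 4 event need not meet the seriousness criteria of Section 9.1.9.

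4. *The inversion.* Take a non-serious grade 4 event with onset on day 60 after the last dose, which is later than 30 days and well inside 6 months. If it is judged unrelated or unlikely, Table 6 requires OnCore entry by the later of 30 days after the reporting period or the next quarterly deadline. If it is judged possible, probable or definite, footnote 3 says no report is required. The event more likely to be due to the supplement has the shorter window.

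5. *Section 9.2.3.2 within itself.* The paragraph opens by requiring every SAE to be faxed and ends by asking for a report on each SAE that occurs. Between these it limits reports after 30 days to related SAEs. Even as a rule for the facsimile alone, the paragraph does not agree with itself.

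**The case against.** Three arguments deserve weight.

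First, Table 6 might govern only extra reporting for the DSMC. Section 9.2.1 does say that its thresholds add to routine data capture. But the same section requires all AEs to be entered in OnCore within its time frames, and Section 10.1 has AEs entered as Section 9.2 describes. Section 9.2.3.1 makes collection of target AEs in follow-up depend on meeting Section 9.2.1 or 9.2.2. Table 6 therefore does bear on what is collected.

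Second, 30 days may be the intended limit for non-serious AEs. The Synopsis, Section 1.3, Section 7.3 and Schedule footnote 2 all use it. The Fact Sheet in Appendix B gives an elimination half-life of 6.8 hours, so new related events after 30 days may well be few. This stands as a reason not to presume that 6 months is right, and as a reason to expect a small effect. It does not remove the contradiction with Section 6.4, nor explain why unrelated grade 4 events have no cut-off.

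Third, Section 9.2.3.2 is an addition to OnCore reporting. Restricting a late facsimile to related SAEs would fit Tables 9 and 10, whose expedited AE reports cover related or possibly related events. This largely stands. A reader might infer that affiliates and the coordinating site will collect different late SAEs, so that counts cannot be compared across sites. The documents do not support that: the Table 6 SAE row requires every SAE in OnCore to 6 months, with no exception for affiliates. What remains is a sentence that does not name the channel it limits.

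**Conclusion.** The protocol contradicts itself on the window for non-serious grade 3–4 AEs believed related to the supplement: 6 months in Section 6.4, 30 days in Table 6 footnote 3 and Schedule footnote 2. Section 9 leans towards 6 months through an undefined term. Table 6 is also inverted for non-serious grade 4 events. The affiliate sentence in Section 9.2.3.2 is a secondary ambiguity.

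A reader might conclude that delayed related grade 3–4 events in general would be lost. That goes too far, since any that are life-threatening, lead to hospitalisation or are otherwise serious remain reportable to 6 months. Nor should the size be put as the share of follow-up days under conflicting rules: that measures calendar time, not events, and would merge two conflicts that concern different events and sites. The documents give no event rates, so the number of reports at issue is unknown and may be small.

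The conclusion rests on current protocol text and on footnote 3 belonging to the related grade 3 and grade 4 cells, as the table shows. The Procedure Manual, which may say more about the facsimile, was not available. Efficacy analyses are not affected. The point is worth correcting because it decides which late safety events are captured and is cheap to settle.

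**What to change.** Reconcile Schedule of Events footnote 2 (Section 6.1), Section 6.4, the opening of Section 9, Table 6 and Section 9.2.3.2 so that each event class has one reporting window, the same at all sites. The sponsor should choose the window for non-serious related grade 3–4 AEs and state it in each of these places; this review does not choose it. If Section 9 keeps AEs of concern as a category, define it or replace it with the grade and attribution used in Section 6.4.

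Revise Table 6 so that related non-serious grade 4 AEs do not have a shorter window than unrelated ones.

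In Section 9.2.3.2, state whether the 30-day limit covers only the facsimile, with all SAEs still entered in OnCore to 6 months, and bring the first and last sentences of that paragraph into line.

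The cost is a few lines of text and, depending on the window chosen, possibly a few more late reports.

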9.2.3.3 Reporting to the FDA

The Study Chair or designee is responsible for providing safety updates to the FDA per the following guidelines. The reporting times refer to the time the study team received knowledge of the AE.

Table 9. FDA Reporting Requirements

UVa PI HELD IND			
Type of Event	To whom will it be reported:	Time Frame for Reporting	How reported?
Life-threatening and/or fatal unexpected events related or possibly related to the use of the investigational agent.*	FDA	Within 7 calendar days of the study team learning of the event	Form FDA 3500A (MedWatch) or narrative
Serious, unexpected and related or possibly related AEs*	FDA	Within 15 calendar days after the study team receives knowledge of the event	Form FDA 3500A (MedWatch) or narrative
All AEs	FDA	Annually	IND annual report

*Applies to AEs/SAEs not identified in [Appendix C](#)

Certain anticipated SAEs will not be reported individually to the FDA in an expedited fashion due to their frequency in the study population independent of study supplement exposure. The events listed in [Appendix C](#) are common in patients receiving the chemotherapeutic agents listed in [Section 3.1](#) and so will instead be reported in aggregate to the FDA using an IND safety report should analysis indicate that the toxicities are occurring more frequently in patients taking genistein.

The Study Chair may also choose to refrain from single-event IND safety reporting should an AE/SAE be related to the subject’s underlying disease. These events are not included in [Appendix C](#) due to the wide range of cancers that may participate in this study. As above, such AE/SAEs will be reported using an IND safety report should aggregate analysis demonstrate increased toxicity associated with genistein treatment.

Single-event IND safety reports submitted to the FDA will be blinded, per permission granted by the agency on 19May2017.

Annual reports to the FDA will include AEs and SAEs collected as described in [Section 9.2.1](#), with the exception of target AEs collected solely for the purposes endpoint analysis. Those target AEs are non-serious grades 1 and 2, any attribution to the study supplement, and non-serious grade 3 with an unrelated or unlikely relationship to the study supplement.

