3.2 Exclusion Criteria

- [1] Known allergy to soy or any soy-based food or supplement
- [2] Unable or unwilling to discontinue consuming prohibited soy-based food or supplements while participating in this study ([Section 4.8.1](#))
- [3] Pre-existing neutropenia or neutrophil qualitative or quantitative disorder ([Section 6.3](#))
- [4] Pre-existing cytopenia or bone marrow failure syndrome
- [5] History of gastric or duodenal ulcers or hyperacidity syndromes
- [6] History of Human Immunodeficiency Virus (HIV)
- [7] Has an active infection requiring systemic therapy
- [8] Planned treatment does not include myelosuppressive chemotherapy
- [9] Enrolled on a therapeutic or supportive care clinical trial within the last 30 days
- [10] Current acute or chronic leukemia diagnosis
- [11] Requires medication dosing via an enteral feeding tube that terminates in the duodenum or jejunum. (Enteral feeding tubes that terminate in the stomach are acceptable for study medication delivery.)
- [12] Pregnant or breastfeeding woman
- [13] Incarceration
- [14] Secondary malignancy, i.e. the cancer for which the patient is presently or will be receiving treatment may not be a malignancy related to prior cancer therapy
- [15] Any condition which might be worsened by estrogen, such as breast cancer, uterine cancer, ovarian cancer, endometriosis or uterine fibroids
- [16] Any condition, in the investigator's opinion, that would compromise patient safety or study outcomes
- [17] Anyone who, in the investigator's discretion, would be unwilling or unable to comply with study procedures

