5.1.7 Expected Adverse Events

The side effects of usage of genistein reported in the literature are mild. The most common effect is abdominal pain (≤ grade 2). This is the only AE that will be considered to be expected for the purposes of this study.

Genistein may have estrogenic properties. Therefore any condition which might be worsened by estrogen, such as breast cancer, uterine cancer, ovarian cancer, endometriosis or uterine fibroids, may also be worsened by administration of genistein. The effect of genistein in someone who is pregnant or breast-feeding is not known.

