9.2.3.4 Reporting to Participating Sites

The Study Chair or designee is responsible for providing safety updates to all participating sites per the following guidelines:

Table 10. Required Reporting to Participating Sites

UVa PI of MULTI-SITE TRIAL			
Type of Event	To whom will it be reported:	Time Frame for Reporting	How reported?
Serious, unexpected and related or possibly related AEs	All Research Sites	Within 15 calendar days after the Study Chair receives knowledge of the event	IND Safety Report (Cover letter, copy of MedWatch or narrative)
Unanticipated Problem	All Research Sites	Within 15 calendar days from the time the Study Chair receives knowledge of the event.	Letter to Site PIs, Copy of MedWatch or narrative

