APPENDIX C: TOXICITIES EXCLUDED FROM SINGLE-EVENT IND SAFETY REPORTING TO THE FDA

See [Section 9.2.3.3](#) for additional information about the submission of these toxicities to the FDA.

Adverse Events	Actinomycin	Carboplatin	Cisplatin	Cyclophosphamide	Daunorubicin	Doxorubicin	Etoposide	Ifosfamide	Topotecan	Vincristine
Myelosuppression	X	X	X	X	X	X	X	X	X	
Anemia	X	X	X	X	X	X	X	X	X	
Leukopenia	X	X	X	X	X	X	X	X	X	X
Neutropenia	X	X	X	X	X	X	X	X	X	
Thrombocytopenia	X	X	X	X	X	X	X	X	X	X
Febrile Neutropenia	X	X	X	X	X	X	X	X	X	
Infection	X	X	X	X	X	X	X	X	X	X
Nausea	X	X	X	X	X	X	X	X	X	X
Vomiting	X	X	X	X	X	X	X	X	X	X
Diarrhea	X	X		X	X	X	X		X	X
Abdominal Pain	X			X	X	X	X		X	X
Anorexia	X			X			X		X	
Mucositis		X			X	X				
Hypersensitivity Reaction		X								
Cardiotoxicity				X	X	X				
Ototoxicity		X	X							
Nephrotoxicity		X	X					X		
Hepatotoxicity	X						X			
Hypomagnesemia		X	X	X						
Hypokalemia		X	X							
Hypocalcemia		X	X							
Hyponatremia		X	X							
Neurotoxicity		X	X					X		X
Neuropathy		X	X							X
Alopecia	X			X	X	X	X	X	X	X

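### The Table 9 footnote exempts Appendix C events from single-event FDA reports whatever their grade or the agent received, and so reaches some serious related abdominal pain and hypersensitivity cases that its rationale does not cover

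*Combined protocol and SAP*

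**What the plan says.** Table 9 in Section 9.2.3.3 has two expedited rows for the FDA. The 7-day row covers "Life-threatening and/or fatal unexpected events related or possibly related to the use of the investigational agent". The 15-day row covers serious, unexpected events that are related or possibly related. Both carry an asterisk, and the footnote reads "Applies to AEs/SAEs not identified in" Appendix C.

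The text below the table gives the reason: these events are left out "due to their frequency in the study population independent of study supplement exposure", being common with the chemotherapy agents listed in Section 3.1. They go to the FDA in aggregate instead, if analysis indicates that they occur more often on genistein.

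Appendix C is a grid of events by agent. It lists "Abdominal Pain" and "Hypersensitivity Reaction" with no grade, seriousness or attribution attached. Section 5.1.7 says of genistein: "The most common effect is abdominal pain (≤ grade 2). This is the only AE that will be considered to be expected". Table 10 (Section 9.2.3.4) requires an IND Safety Report to all research sites for "Serious, unexpected and related or possibly related AEs" and has no Appendix C footnote.

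**The concern.** An exemption based on background frequency suits events that chemotherapy produces often and that say little about the supplement. The footnote reaches further because it works on the name of the event only. It takes in an event that the protocol itself attributes to genistein, at grades the protocol does not expect. Read literally, it also takes in an event in subjects whose chemotherapy is not marked for it.

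At stake is how soon the FDA sees a serious case that the investigator considers at least possibly related to genistein. For these two kinds of case, the 7-day or 15-day report is replaced by the annual report or by a conditional aggregate report.

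**Working it through.** There is no stated figure to reproduce. The check sets the rules side by side, counts the marks in Appendix C, and adds one illustration.

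**1. Abdominal pain by grade.** Take a serious case judged related or possibly related, with expectedness as in Section 5.1.7.

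- Grade 2 or lower: expected for genistein, so already outside both rows of Table 9. The Appendix C entry changes nothing.
- Grade 3 or higher: not covered by the expected grade, so inside Table 9 until the footnote removes it.

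For related serious events, the only practical effect of the entry is therefore to exempt the grades that Section 5.1.7 does not expect.

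**2. Marks in Appendix C** (qualifying agents are the nine in Section 3.1).

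- Abdominal pain: actinomycin, cyclophosphamide, daunorubicin, doxorubicin, etoposide and topotecan, which is 6 of 9, plus vincristine.
- Hypersensitivity: carboplatin only, 1 of 9.

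**3. Would matching the exemption to the agent received be enough?** A regimen needs at least two of the nine agents, giving 9 × 8 / 2 = 36 possible pairs.

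- Abdominal pain: only pairs drawn from carboplatin, cisplatin and ifosfamide avoid a marked agent, 3 × 2 / 2 = 3 pairs. The other 33 contain one, and adding vincristine adds another mark. Agent matching alone leaves the problem with Section 5.1.7 almost untouched.
- Hypersensitivity: pairs without carboplatin number 8 × 7 / 2 = 28 of 36. Agent matching removes the exemption for all of these.

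These are counts of possible pairs, not proportions of patients; the documents do not give the regimen mix.

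**4. Routes that remain for an exempted case.**

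| Route | Timing | Appendix C exemption |
|---|---|---|
| OnCore/DSMC (9.2.1) | SAE entry in 24 hours, documents in 7 days | None |
| Affiliate site to sponsor (9.2.3.2) | 24 hours | None |
| UVa IRB (9.2.2) | 7 days if serious and unexpected for the population | None |
| Participating sites (Table 10) | 15 days | None |
| FDA, single event (Table 9) | 7 or 15 days | Exempt |
| FDA, aggregate | If analysis shows an excess; no threshold, method or timetable in 9.2.3.3 | Replacement route |
| FDA, annual report | Yearly | Included |

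**5. Illustration of the aggregate route.** Assumption, not in the documents: an excess means a one-sided 5% exact sign test on subjects who have the event in only one condition.

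- With no placebo-only subjects, 5 genistein-only subjects are needed: 0.5^5 = 0.031.
- With 1 placebo-only subject, 7 are needed (p = 0.035). With 2, 9 are needed (p = 0.033).

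For 44 subjects and no placebo-only events, binomial probabilities are:

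| True rate on genistein | At least 1 case | At least 5 cases |
|---|---|---|
| 2% | 59% | 0.2% |
| 5% | 90% | 6.7% |
| 10% | 99% | 45% |
| 15% | 99.9% | 81% |

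The rates are a range for illustration. At the lower rates, one or more cases would probably occur without triggering an aggregate report under such a test.

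**The case against.** The strongest reply is that Appendix C is a grid. Its columns would have little purpose if the exemption ignored the agent, so a reader may take hypersensitivity as exempt only with carboplatin. That reading is possible and would remove the second kind of case. But neither the footnote nor the text states it, and it does not help with abdominal pain.

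Abdominal pain is also marked for most qualifying agents, which is the background frequency that the sponsor invokes, and one blinded case is hard to interpret. This stands as a reason for some exemption. However, the Table 9 rows apply only once the event has been judged at least possibly related to the agent.

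Section 9.1.7 lets expectedness of SAEs take the study population into account. On that basis, severe abdominal pain might count as expected and never enter Table 9. The section does not say which basis governs Table 9, so the point about abdominal pain assumes the genistein-based definition in Section 5.1.7.

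Four stronger readings are tempting, but the documents do not support them:

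- *Hypersensitivity is a named risk of the supplement.* Section 5.1.7 makes abdominal pain the only expected event. Soy allergy appears as an exclusion ("Known allergy to soy or any soy-based food or supplement") and as the Fact Sheet's contraindication. These concern patients who are already allergic. The safety data sheet classifies no component as a sensitiser.
- *Serious cases would not be expedited at all.* Only the FDA single-event route is affected.
- *Tables 9 and 10 cannot both be followed.* They have different recipients, and Table 10 accepts a narrative in place of a MedWatch copy.
- *The aggregate review could not detect these events.* That depends on a formal test, which the protocol does not specify.

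**Conclusion.** The concern holds in limited form. Followed literally, the footnote withholds from single-event FDA reporting (a) serious, related abdominal pain above grade 2, which does not sit with Section 5.1.7, and (b) serious, related hypersensitivity in a subject not given carboplatin, which does not fit the rationale of events common with the subject's chemotherapy. Part (a) assumes that Table 9 judges expectedness against genistein. Part (b) assumes the footnote's wording and not an unstated reading by column.

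The size is modest. The documents give no rate for either event; serious cases among 44 subjects should be few. The gap is confined to one recipient, and no endpoint, estimate or analysis changes. It still merits correction, because the replacement route is conditional and undefined in that section and the change is one of wording.

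**What to change.** 1. Reword the Table 9 footnote so that the exemption applies only to an event marked in Appendix C for an agent that the subject received in that cycle.
2. Reconcile the abdominal pain entry with Section 5.1.7, so that related serious events above the grade expected for genistein stay in single-event reporting. Either remove the entry or state the limit. For related events the two come to nearly the same thing, since lower grades are already expected.
3. Leave Table 10 without an exemption, and state that reports to sites do not depend on Appendix C. Copying the exemption there would reduce the safety information that sites receive.

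The cost is a protocol wording change and a small number of additional single-event reports. Section 9.2.3.3 already provides for these to be sent blinded, so the trial's blinding is not affected.
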